### **3.2.3.2. Pharmacokinetics**

RVT-1401 exhibited non-linear pharmacokinetics (PK) following single SC administration across doses ranging from 0.5 mg/kg to 765 mg. The non-linearity is consistent with RVT-1401 exhibiting target mediated disposition PK. In addition to single dose administration, RVT-1401 has also been administered weekly SC for 4 weeks at doses of 340 and 680 mg. The observed mean concentration-time profile following the first and last dose were generally similar, rising to peak concentration between 2 and 3 days after the dose and then declining beginning 4 days after administration up until the next dose. The rate of elimination was more rapid following administration of 340 mg compared to 680 mg, indicative of target mediated drug disposition. Across both dosing cohorts there was accumulation in the exposure measures of Cmax and AUC(0-168). The accumulation in Cmax and AUC(0-168) in the 340 mg cohort was 7 and 8.7-fold respectively between the first and last dose, and 2.23 and 2.64, respectively in the 680 mg cohort. There was large variability in Cmax and AUC(0-168) after the first dose of 340 mg, whereas there was less variability following first SC dose of 680 mg, consistent with what was observed in single dose data. Overall there was reduction in the inter-individual variability around Cmax and AUC(0-168) after subsequent doses. Following the last dose in the 680 mg cohort, the profile shows characteristics of target mediated drug disposition, with a linear elimination phase from ~96 hours to 168 hours after the last dose, at which time the elimination was very rapid from 168 hours to 336 hours post dose. Exposures increased more than dose proportionally when comparing week four of the 340 mg dose to exposures following the 680 mg SC dose.

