## **5. STUDY DESIGN**

### **5.1. Overall Design**

This is a Phase 2a, randomized, double-blind, placebo-controlled study with an OLE designed to investigate the safety, tolerability, PK, PD, and efficacy of RVT-1401 (340 mg/weekly and 680 mg/weekly) vs placebo in AChR antibody positive MG patients. Following a 6-week double-blind, placebo-controlled phase, all participants will have the option to enter an OLE where they will receive an additional 3 doses of 340 mg RVT-1401 every 2 weeks for 6 weeks. The study designs are illustrated in Section 5.2.

Safety, PK, PD, and clinical assessments will be collected throughout the study. Refer to Section 8.1 and 8.2, Time and Events Tables.

Optional home visits will be offered to collect (at a minimum) blood samples, vital signs, and review adverse events and concomitant medications.

Each participant will participate in the study for up to approximately 21 weeks: a 3-week screening period, and a 6-week double-blind, placebo-controlled treatment period. Participants who choose not to enroll into the OLE will continue into a 12-week follow-up period. Those who choose to enroll into the OLE will receive treatment in a 6-week OLE period (3 additional doses, every 2 weeks), and a 6-week follow up period. The study duration is the same whether a participant continues directly into the 12-week follow-up period or enrolls into the OLE.

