### **Open-Label Extension**

If the participant is eligible and consents to enroll into the OLE, starting at Week 8 an additional 3 doses of 340 mg RVT-1401 will be administered over a 6-week period (every 2 weeks) followed by a 6-week follow up period.

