5.1. Analysis Populations

In accordance with guidance from the International Conference on Harmonisation of Technical Requirements for Registration of Pharmaceuticals for Human Use (ICH) *Statistical Principles for Clinical Trials E9* (1998), the following analysis populations will be used for all statistical analyses:

- The full analysis set (FAS) includes all randomized subjects who receive at least one dose of randomized study medication with at least one valid post-treatment value. The FAS is used for all efficacy analyses.
- The per-protocol set (PPS) includes all FAS subjects who do not have significant protocol violations, where a significant protocol violation is one that has the potential to affect analysis conclusions. Final determinations of significant protocol violations will be made at the final blinded data review meeting in accordance with guidance from ICH E9 (Statistical Principles).
- The safety analysis set (SAF) includes all subjects who received at least one dose of study medication. The SAF is used for all safety analyses.

- The Pharmacokinetic (PK) analysis set includes all subjects who undergo PK sampling and have evaluable concentration-time data for analysis.
- The Pharmacodynamic (PD) analysis set includes all subjects who received at least 1 dose of study medication and have a baseline PD measurement and at least 1 post-baseline PD measurement.
- The Open-label Extension (OLE) analysis set includes all subjects who enroll in the OLE study phase and receive at least 1 dose of study medication in the OLE. The OLE subjects will be summarized by actual treatment in the double-blind treatment period for safety and PK analyses and by randomized treatment assigned in the double-blind treatment period for other analyses based on the OLE population.

Solely to understand the influence of dropouts on study conclusions, the FAS will be partitioned into completers and dropouts.

Efficacy analysis will be done as randomized. Safety analysis will be done as treated. In the event the administered dose level is not consistent throughout the double-blinded period, the as treated arm will be determined by the highest dose level received during the double-blinded treatment period.

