10.1.5. Treatment-Emergent Adverse Events

10.1.5.1. Definition of Treatment-Emergent

Adverse events will be classified by study part according to the following:

- Pre-treatment: AEs that either started prior to the date of the first dose of study drug or had no recorded start date and the stop date is prior to the first dose of study drug.
- Treatment-emergent: AEs that either started on or after the date of the first dose of study drug and on or before the date of 6 weeks (42 days) post the last dose of study drug or had no recorded start date and the stop date is not before the first dose of study drug.
- Post-treatment: AEs that started after the date of 6 weeks (42 days) post the last dose of study drug.
- OLE treatment-emergent: AEs that either started on or after the date of the first dose of study drug in the OLE.

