10.1.6. Summaries of Adverse Events

All AE summaries will be provided separately for the double-blind treatment period and the follow-up period as well as the OLE treatment period and OLE follow-up period. Double-blind treatment period AE summaries will present treatment-emergent AEs which occurred before study drug administration during OLE study period or before the primary lock date, whichever comes first. Follow-up period AE summaries will present post-treatment AEs, OLE treatment period AE summaries will present OLE treatment-emergent AEs which occur before or on week 12 visit and OLE follow-up period AE summaries will present OLE post-treatment AEs. Pre-treatment AEs will be listed.

Overall summaries of treatment-emergent AEs by treatment group will be provided to include the number and percentage of subjects who:

1. Had any AE,
2. Had any Grade 3 or higher AE,
3. Had any treatment-related AE,
4. Had any Grade 3 or higher treatment-related AE,
5. Had any SAE,
6. Had any treatment-related SAE,
7. Permanently discontinued from study drug due to an AE, and
8. Died.

Summaries (number and percent of subjects) of treatment-emergent adverse events (by SOC, and PT) will be provided by treatment group for the following:

- All AEs,
- All Grade 3 or higher AEs,
- All treatment-related AEs,
- All Grade 3 or higher treatment-related AEs,
- All SAEs,
- All treatment-related SAEs,
- All AEs that leading to permanently discontinued from study drug.

Multiple events will be counted once only per subject in each summary. For data presentation, SOC will be ordered alphabetically, with PT sorted by decreasing frequency in

the combined RVT-1401 column. Treatment period and follow-up period AE summaries will be provided for the SAF analysis population. Open-label extension AE summaries will be provided for the OLE analysis population. Whole study AE summaries include the double blinded period, OLE period and follow up will be provided for below 3 tables:

- Overall summaries of treatment-Emergent AEs
- Treatment-emergent AEs by SOC and PT
- Serious treatment-emergent AEs by SOC and PT

In addition to the by-treatment AE summaries, data listings will be provided for the following:

- Pre-treatment AEs
- Treatment-emergent AEs
- Post-treatment AEs
- OLE treatment-emergent AEs
- SAEs
- Liver events
- AEs leading to discontinuation or interruption of study drug
- Deaths
- Grades 2-4 albumin events

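### The OLE treatment-period AE table closes on the day of the last OLE dose, and the whole-study AE tables appear to count placebo switchers' open-label events under placebo

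*SAP*

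**What the plan says.** **Dosing.** Protocol 5.1 (Open-Label Extension) says that "starting at Week 8 an additional 3 doses of 340 mg RVT-1401 will be administered over a 6-week period (every 2 weeks". Protocol 5.1 (Overall Design) describes a "6-week OLE period (3 additional doses, every 2 weeks), and a 6-week follow up period".

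**AE classes.** SAP 10.1.5.1 defines four: pre-treatment, treatment-emergent, post-treatment and OLE treatment-emergent. A treatment-emergent AE starts between the first dose and a limit set as "on or before the date of 6 weeks (42 days) post the last dose of study drug"; post-treatment AEs start after that limit. OLE treatment-emergent AEs start on or after the first OLE dose, and the class has no end date.

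**OLE tables.** SAP 10.1.6 says that "OLE treatment period AE summaries will present OLE treatment-emergent AEs which occur before or on week 12 visit". It fills the OLE follow-up table with OLE post-treatment AEs, a class that 10.1.5.1 does not contain.

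**Whole-study tables.** SAP 10.1.6 adds: "Whole study AE summaries include the double blinded period, OLE period and follow up will be provided for below 3 tables". These are the overall TEAE summary, TEAEs by SOC and PT, and serious TEAEs by SOC and PT. The section states neither a population nor a column rule for them.

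**Columns.** SAP 5 lists placebo, 340 mg, 680 mg and combined RVT-1401. SAP 5.1 says that "The OLE subjects will be summarized by actual treatment in the double-blind treatment period for safety and PK analyses" and sets the as-treated arm from doses received in the double-blind period. SAP 5.3 groups the safety set by actual treatment received. No rule assigns an AE to the treatment being taken at onset.

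**The concern.** A treatment-period AE table should cover the time on drug. This one gives the first two OLE doses a full dosing interval and the third dose a single day. Protocol 3.2.3.2 reports concentrations in healthy participants "rising to peak concentration between 2 and 3 days after the dose", so the days of highest exposure after the third dose lie outside the table. A programmer also cannot tell from the SAP where those later AEs belong.

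In the whole-study tables, a serious event in a placebo participant who is taking open-label RVT-1401 would be printed as a placebo event. It would not be counted in the combined drug column.

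Safety and tolerability is a primary objective, and the OLE objective covers all study endpoints. With about 7 participants per arm, moving one participant shifts an arm's percentage by 1/7, or about 14 points.

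**Working it through.** **1. Timeline.** The Time and Events tables equate Week 6 with Day 36, so Week w = Day 7(w − 1) + 1.

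- OLE doses: Weeks 8, 10, 12 = Days 50, 64, 78.
- Week 14 = Day 92; Week 18 = Day 120.
- Check against the protocol: last dose at Week 12 + 6 weeks of follow-up = Week 18, and 3 weeks of screening + 18 = 21 weeks, which agrees with "Each participant will participate in the study for up to approximately 21 weeks".

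**2. Coverage of the OLE treatment-period table.**

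- Days covered: Day 50 to Day 78 = 78 − 50 + 1 = 29.
- Three 14-day intervals: Day 50 to Day 91 = 42 days. This matches the six-week OLE treatment period named in SAP 6.1 and 6.2.1, counted from the first OLE dose as SAP 5 directs.
- Omitted: Days 79 to 91 = 13 days; 13/42 = 31%.
- If concentrations peak 2 to 3 days after the dose, as in healthy participants, the peak after the third dose falls on Days 80 to 81, after the cut-off.
- The ±2-day visit window moves the Week 12 visit between Days 76 and 80. Dose and cut-off move together, so the result does not change.

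**3. Where AEs after Day 78 go.** The undefined class leaves two readings.

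- If it means anything after the Week 12 visit, AEs on Days 79 to 120 go to the OLE follow-up table.
- If it follows the general rule of more than 42 days after the last dose, it begins after Day 78 + 42 = Day 120, the nominal final visit. AEs on Days 79 to 120 (42 days) are then in neither OLE period table.

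**4. The double-blind table as a comparator.** For OLE participants, SAP 10.1.6 stops the double-blind table before the first OLE dose (or at the primary lock, if earlier). The Week 6 dose on Day 36 therefore contributes Days 36 to 49, which is 14 days. The third OLE dose contributes 1.

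**5. Whole-study tables.**

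- A placebo switcher is followed on or after the first active dose from Day 50 to Day 120: 71 of 120 nominal days (59%). Under the double-blind grouping, all of it counts as placebo.
- The combined column then holds 14 participants, although up to 21 would have received RVT-1401.
- Illustration only, because the documents give no AE risks. Assume all 7 placebo participants enter the OLE, the periods are independent, the AE risk on true placebo is 30%, and the risk on OLE drug is 10% to 50%. The placebo column then shows 1 − 0.7 × 0.9 = 37% to 1 − 0.7 × 0.5 = 65%, against 30% on placebo alone. With 20% to 40% on placebo and 20% to 60% on OLE drug, it shows 1 − 0.8 × 0.8 = 36% to 1 − 0.6 × 0.4 = 76%.

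**The case against.** **The Week 12 boundary may be deliberate.** Six weeks of follow-up ending at Week 18 start at Week 12, so the cut-off is a coherent calendar label. That stands as an explanation. It does not fit SAP 5, which starts the OLE period at the first OLE dose, or the six-week OLE treatment period in SAP 6.1 and 6.2.1, which on that start ends at Week 14. It also leaves the follow-up class undefined.

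**The column assignment is inferred.** This also stands. SAP 10.1.6 does not state columns for the whole-study tables, the SAP 5.1 sentence on OLE subjects concerns the OLE analysis set, and table shells are not among the documents. The inference is the natural one, because SAP 5 lists no switcher column and the as-treated rule looks only at double-blind doses.

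**Much of the information survives elsewhere.** The OLE tables, grouped by double-blind arm, already show switchers' AEs through Week 12 in their placebo column. Listings of OLE treatment-emergent AEs and SAEs have no Week 12 cut-off. Injection site reactions are assessed about 10 minutes after dosing and summarised separately, so immediate reactions to the third dose are captured.

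**Stronger readings that the documents do not support.**

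- A reader might infer that the placebo-controlled AE comparison is biased. It is not: the double-blind tables exclude events after OLE dosing starts.
- A reader might infer that drug-exposed events are concealed. They remain in the listings.
- A reader might infer that the OLE follow-up AE rate is overstated. That holds on only one of the two readings in step 3.
- A reader might take the general 42-day rule as the right OLE cut-off. It reaches Day 120 and would nearly empty the planned OLE follow-up table. For OLE participants the double-blind table does not run the full 42 days either.

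**Conclusion.** The point holds for two sets of tables. First, the OLE treatment-period AE table omits 13 of 42 nominal dosing-interval days, all after the last dose, and the SAP does not settle whether those AEs appear in the other OLE period table. This follows directly from the stated schedule and cut-off; only the timing of the peak is carried over from healthy participants. Second, the three whole-study tables would, on the SAP's general grouping rules, count placebo switchers' open-label AEs and SAEs under placebo. If the drug raises AE risk, that draws the placebo and drug columns together. This part rests on inference about the columns, and its size depends on how many placebo participants enter the OLE and on AE risks that the documents do not give. The 37% to 65% range shows scale and is not an estimate. The randomised double-blind AE comparison is not affected. The changes are worth making because they are cheap and safety is a primary objective.

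**What to change.** **SAP 10.1.5.1 and 10.1.6, OLE period tables.**

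- Give OLE treatment-emergent AEs an end date, and close the OLE treatment-period table there: the end of the third dosing interval, expressed as the Week 14 visit or as 14 days after the last OLE dose.
- Define OLE post-treatment AEs as those starting after that point, so that every OLE AE falls in exactly one period table.

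Check in nominal days, counting Day 92 as treatment: Days 50 to 92 (43 days) plus Days 93 to 120 (28 days) = 71 days, with no gap or overlap.

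**SAP 10.1.6, whole-study tables.**

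- State the population and the columns.
- Close the placebo column at the first OLE dose.
- Show switchers' later AEs in a column for placebo to RVT-1401 340 mg every 2 weeks, and count them in a column for any RVT-1401 exposure.

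**Cost.** SAP wording and table shells only, with no new data. There will be one or two extra columns, a higher OLE treatment-period AE count, and a shorter OLE follow-up window (Weeks 14 to 18). The whole-study columns will also cover unequal time: for a switcher, 49 nominal days before the first OLE dose and 71 from it onward. Crude percentages should be read with that in mind.

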10.1.7. Injection Site Reactions

Injection site reactions will be summarized (number and percentage of subjects) by symptom and toxicity grade and provided by treatment group. Multiple events will be counted once only per subject in each summary. Additionally, a summary of the number of subjects who experienced at least 1 injection site reaction during the study and at each visit will be provided for the SAF analysis population. No inferential statistics will be generated. Injection site reactions will also be listed.

10.2. Laboratory Evaluations

Descriptive statistics (sample size, mean, standard deviation, median, Q1, Q3, minimum and maximum) of baseline, post-baseline, and change from baseline central laboratory values collected for each laboratory parameter will be provided by treatment group for all scheduled visits. If result contains '<', then the result for continuous summaries will be the value divided by 2, and if the result contains '>' then the result for continuous summaries will be the value plus 0.01 for analysis. The listings will display the value as collected.

Hematology, clinical chemistry, urinalysis and additional parameters to be tested by central laboratory are listed below:

Hematology

Platelet count	Red Blood Cell Indices:	Automated White Blood Cell Differential:
Red blood cell count	Mean corpuscular volume	Neutrophils
White blood cell count (absolute)	Mean corpuscular hemoglobin	Lymphocytes
Reticulocyte count	Mean corpuscular hemoglobin concentration	Monocytes
Hemoglobin		Eosinophils
Hematocrit		Basophils

Clinical Chemistry

Blood urea nitrogen (BUN)	Potassium	AST (SGOT)	Total and direct bilirubin
Creatinine	Chloride	ALT (SGPT)	Uric Acid
Glucose fasting [on Day 1 (baseline) and Week 7 only]	Total carbon dioxide (CO ₂)	Gamma glutamyl transferase (GGT)	Albumin*
Sodium	Calcium (corrected)	Alkaline phosphatase (ALP)	Total Protein
Serum complement (CH50, C3)	Immunoglobulin M (IgM)	Immunoglobulin A (IgA)	Immunoglobulin G (IgG)

Routine Urinalysis

Specific gravity, pH
Glucose, protein, blood, and ketones by dipstick
Microscopic examination (if blood or protein is abnormal)

Other tests

QuantiFERON®-TB Gold
Viral Serology [HIV1/HIV2, hepatitis B (HBsAg), hepatitis B (core antibody), hepatitis C (Hep C antibody)]
Follicle-stimulating hormone (as needed for confirmation of postmenopausal status)
Pregnancy tests: serum test at screening, Week 18, and early withdrawal and urine dipstick pre-dose at other time points. Positive urine tests should be confirmed with a serum test.

* Albumin collected from central lab will be graded to Grade 1 to 3 by CTCAE version 5.0.

Additionally, summaries (number and percentage of subjects) of shifts from baseline central laboratory value (low, normal, or high) to post-baseline value (low, normal, or high) at each scheduled post-baseline visit for each parameter will be provided by treatment group.

Albumin from central laboratory will be graded according to CTCAE v5.0 as below. The highest CTCAE grade for each visit will be summarized using a shift table to assess changes from baseline. Grading of albumin will only be based on the following numeric values, (note this may lead to a discrepancy with the protocol-defined Grade 2 event since the protocol also involves signs/symptoms attributable to hypoalbuminemia and not just on the lab value):

Grade 1	Grade 2	Grade 3
<LLN - 3 g/dL; <LLN - 30 g/L	<3 - 2 g/dL; <30 - 20 g/L	<2 g/dL; <20 g/L

Central and local laboratory clinical chemistry, hematology, and urinalysis values will be listed and flagged high or low relative to the normal range where appropriate. Summaries of laboratory data will be provided for the SAF analysis population. No inferential statistics will be generated.

Because “exacerbations” of pre-existing abnormalities in laboratory analytes are examined using clinical judgment and are reported as TEAEs, additional analysis on treatment-emergent abnormal values is limited to subjects with values that are normal prior to dosing and abnormal after dosing.

Adverse events of special interest also treatment-emergent abnormal values TEAVs in laboratory parameters related to liver function tests, specifically ALT, AST, bilirubin, and ALK.

Potentially clinically significant values in laboratory analytes will be examined in accordance with the table of values or changes of potential clinical significance in this SAP. Proportions of subjects in each treatment group who meet the criteria will be analyzed.

Laboratory data will be summarized by Baseline and change from Baseline to each scheduled assessment time with descriptive statistics.

Liver function tests have additional monitoring for this study.

To explore the potential for drug-induced liver injury consistent with *Guidance for Industry “Drug-induced liver injury: premarketing clinical evaluation”* (CDER, CBER, July 2009), subjects will be summarized and listed who meet the following criteria:

1. Elevations in either AST or ALT of at least 3-times the upper limit of normal, and
2. An accompanying abnormal bilirubin.

Additionally, a summary and listing will be examined for subjects with elevations in either AST or ALT of at least 3-times the upper limit of normal, regardless of bilirubin.

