## 7.3. Blinding

This will be a double-blind study. The investigator and study site will also remain blinded to the IgG, albumin, total protein, alkaline phosphatase (ALP), and anti-AChR antibody data post screening as this could potentially unblind them. An unblinded Medical Monitor will review this lab data on an ongoing basis for safety. In order to maintain the blind of which treatment subjects received during the double-blind phase of the study, these labs will continue to be blinded to the investigator and study site in the OLE.

The following will apply throughout the study:

- The Investigator or treating physician may unblind a participant's treatment assignment **only in the case of an emergency** OR in the event of a serious medical condition when knowledge of the study treatment is essential for the appropriate clinical management or welfare of the participant as judged by the Investigator. Emergency unblinding will be available via the IWRS or via the unblinded pharmacist.
- The Investigator should make every effort to first contact the Medical Monitor or appropriate study personnel to discuss options **before** unblinding the participant's treatment assignment.
- If the Medical Monitor is not contacted before the unblinding, the Investigator must notify the Sponsor as soon as possible after unblinding.
- The date and reason for the unblinding (the event or condition which led to the unblinding) must be fully documented in the eCRF

A participant will be withdrawn if the participant's treatment code is unblinded by the Investigator or treating physician.

The Sponsor or their designee may unblind the treatment assignment for any participant with a SAE. If the SAE requires that an expedited regulatory report be sent to one or more regulatory agencies, a copy of the report, identifying the participant's treatment assignment, may be sent to Investigator in accordance with local regulations.

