#### **Clinical Chemistry**

Blood urea nitrogen (BUN)	Potassium	AST (SGOT)	Total and direct bilirubin
Creatinine	Chloride	ALT (SGPT)	Uric Acid
Glucose fasting [on Day 1 (baseline) and Week 7 only]	Total carbon dioxide (CO 2 )	Gamma glutamyltransferase (GGT)	Albumin
Sodium	Calcium (corrected)	Alkaline phosphatase (ALP)	Total Protein
Serum complement (CH50, C3)	Immunoglobulin M (IgM)	Immunoglobulin A (IgA)	
Immunoglobulin G (IgG)			

Since changes in ALP, total protein and albumin level can potentially unblind the investigator to which dose the participant has been randomized to; values for ALP, total protein, and albumin levels will be blinded to the site. An unblinded Medical Monitor will review this lab data on an ongoing basis for safety.

NOTE: Details of Liver Chemistry Stopping Criteria and Follow-Up Procedures are given in Appendix 2: Liver Safety Required Actions and Follow up Assessments.

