## 11.1. Definition of Adverse Events

An AE is any untoward medical occurrence in a participant or clinical investigation participant, temporally associated with the use of a medicinal product, whether or not considered related to the medicinal product.

An AE can therefore be any unfavorable and unintended sign (including an abnormal laboratory finding), symptom, or disease (new or exacerbated) temporally associated with the use of a medicinal product.

Events meeting the definition of an AE **include but are not limited to**:

- Any clinically significant, new or worsened, abnormal laboratory test results (hematology, clinical chemistry, or urinalysis) or other safety assessments (e.g., ECGs, radiological scans, vital signs measurements). Clinical significance is determined based on the medical and scientific judgement of the Investigator.
- Exacerbation of a chronic or intermittent pre-existing condition including an increase in frequency and/or intensity of the condition.
- Signs, symptoms, or the clinical sequelae of a suspected interaction (e.g. with medications or food).
- Signs, symptoms, or the clinical sequelae of a overdose of either investigational product or a concomitant medication (overdose without an AE should be reported as a protocol deviation).

Events that **do not** meet the definition of an AE include:

- Anticipated day-to-day fluctuations of pre-existing condition(s), including the disease under study, that do not represent a clinically significant exacerbation or worsening.
- Abnormal or worsening laboratory, imaging, or other safety findings that are not clinically significant.
- Medical or surgical procedures (e.g., endoscopy, appendectomy); the condition that leads to the procedure is an AE.
- Situations where an untoward medical occurrence did not occur (social and/or convenience admission to a hospital).

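### The reason SAP 10.2 gives for counting treatment-emergent abnormal values only in baseline-normal participants does not hold for site-blinded ALP, total protein and IgG

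*SAP*

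**What the plan says.** SAP 10.2 restricts one laboratory output: "additional analysis on treatment-emergent abnormal values is limited to subjects with values that are normal prior to dosing and abnormal after dosing". The same sentence gives the reason, which is that exacerbations of "pre-existing abnormalities in laboratory analytes are examined using clinical judgment and are reported as TEAEs". SAP 10.2 then names liver treatment-emergent abnormal values (TEAVs) of special interest, "specifically ALT, AST, bilirubin, and ALK"; I read the last of these as ALP.

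Protocol 11.1 says who decides whether a laboratory change is an adverse event: "Clinical significance is determined based on the medical and scientific judgement of the Investigator".

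Protocol 7.3 limits what that person can see: "The investigator and study site will also remain blinded to the IgG, albumin, total protein, alkaline phosphatase (ALP), and anti-AChR antibody data post screening". The clinical chemistry part of Protocol 8.4.4 repeats this for three of the analytes: "values for ALP, total protein, and albumin levels will be blinded to the site". The blinding does not end with the double-blind phase, since "these labs will continue to be blinded to the investigator and study site in the OLE". The safeguard offered is that "An unblinded Medical Monitor will review this lab data on an ongoing basis for safety".

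**The concern.** The restriction assigns worsening from an abnormal baseline to adverse event reporting. That works only if the person reporting adverse events can see the value. For the analytes blinded because they could reveal treatment, the investigator cannot see it, so the SAP relies on a report that the protocol's own blinding largely prevents.

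Change in clinical laboratory values is part of the primary safety endpoint (Protocol 4). What is at stake is whether the report can say how many participants in each arm worsened on these analytes, including those who started abnormal. Such participants can be enrolled. Exclusion criterion 7 removes only abnormalities that the investigator considers clinically significant, unresolved at baseline and a threat to participation. IgG has an eligibility floor of 6 g/L, and no limit is given for ALP or total protein.

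**Working it through.** The plan states no figure on this point, so the check sets the sections side by side.

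**Step 1. Does the reason hold?** SAP 10.2 relies on clinical judgement, Protocol 11.1 gives that judgement to the investigator, and Protocol 7.3 blinds the investigator after screening. SAP 5.2 takes the last value before first dose as baseline, normally Day 1, so the investigator usually sees the screening value but neither the baseline nor anything later. The reason fails for IgG, albumin, total protein and ALP. Anti-AChR antibody is also blinded, but it is a pharmacodynamic endpoint and is not among the safety laboratory parameters in SAP 10.2.

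**Step 2. Does another output count the worsening?** For a participant who starts abnormal and moves further in the same direction:

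| Analyte | TEAV count | Investigator can judge the value | Low/normal/high shift table | Other participant-level output | Group-level output |
|---|---|---|---|---|---|
| ALP | Left out | No | Category unchanged | None confirmed | Change from baseline |
| Total protein | Left out | No | Category unchanged | None confirmed | Change from baseline |
| IgG | Left out | No | Category unchanged | None confirmed | Change and percent change by visit (SAP 12) |
| Albumin | Left out | No | Category unchanged | CTCAE v5.0 grade shift table (SAP 10.2); Grades 2-4 listing (SAP 10.1.6) | Change from baseline |

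Albumin is therefore counted whenever its grade rises, whatever the baseline, though not when it falls within a grade. The liver-injury screen in SAP 10.2 uses AST, ALT and bilirubin, so it does not cover ALP.

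**Step 3. What cannot be settled from the text.** SAP 10.2 also promises the proportion of participants with potentially clinically significant values or changes, by criteria in a table. That table is not in the supplied text, so its coverage of these analytes is unknown. Protocol 6.9.4 on albumin monitoring has a heading but no visible content, so an albumin reporting route may exist there.

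**Step 4. Illustration for IgG.** Inputs: the 6 g/L floor (Protocol 6.3) and the expected falls of 65-70% for 340 mg weekly and 75-80% for 680 mg weekly (Protocol 3.2.2). Value reached = 6 × (1 − fall):

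- 65%: 6 × 0.35 = 2.1 g/L
- 70%: 6 × 0.30 = 1.8 g/L
- 75%: 6 × 0.25 = 1.5 g/L
- 80%: 6 × 0.20 = 1.2 g/L

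If 6 g/L is below the laboratory's lower limit (an assumption; the documents do not give the limit), this participant is outside the TEAV count and stays in the low category. The fall still enters the IgG percent-change analyses.

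**Step 5. Weight of one participant.** With 21 participants randomised 1:1:1 there are about 7 per arm, and 1/7 = 14%. The documents give no rate of abnormal baselines, so the number affected cannot be calculated.

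**The case against.** The strongest reply is that the rule covers only an additional analysis. Participants with abnormal baselines remain in the change-from-baseline summaries, the shift tables and the flagged listings. Percent change in total IgG is the primary efficacy endpoint (SAP 9.1) and is also analysed by visit. The Medical Monitor reviews the blinded values throughout. ALT, AST and bilirubin are not blinded, and the SAP's summaries of AST or ALT elevation have no baseline restriction. All of this stands, and it confines the point to participant-level counts.

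The count of potentially clinically significant values could also fill part of the gap. That is fair, but its coverage cannot be confirmed from the supplied text.

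Two stronger readings are tempting. A reader might infer that worsening in these participants goes unseen or can never become an adverse event. The documents do not support that: the Medical Monitor sees the values, an investigator can still report signs or symptoms, and Protocol 3.3.1 expects hypoalbuminemia to be treated at the investigator's discretion, so some information must be able to reach the site. What is absent from the visible text is a stated route from the Monitor's review into the adverse event data.

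A reader might also infer that the rule biases the drug-placebo safety difference toward zero. That is not supported either. Baseline status is fixed before dosing, so if the denominator is restricted in the same way, the comparison is valid for a narrower group. Dilution would need an all-participant denominator, and the SAP states none. The Phase 1 evidence of little change on placebo concerns IgG and albumin. For ALP and total protein the documents say only that changes could unblind, with no direction or size.

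**Conclusion.** The point holds for ALP, total protein and participant-level counts of IgG. For these the SAP's only stated reason for the baseline-normal rule conflicts with Protocol 7.3 and 11.1, and the three-category shift table does not close the gap. ALP is the most important, being both blinded and a named liver parameter of special interest. Albumin is largely covered.

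The effect is limited to counts of participants who worsen. No value goes unlisted, and the primary IgG analysis is untouched. The size and direction of any effect on the safety comparison are unknown. The conclusion assumes that the unseen table of potentially clinically significant values does not already count worsening in these analytes, and that no route from the Medical Monitor to the adverse event data is set out in text that is not visible.

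**What to change.** In SAP 10.2, for site-blinded ALP, total protein and IgG, count treatment-emergent worsening from central-laboratory values whatever the baseline category:

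- ALP: a rise of at least one CTCAE v5.0 grade from baseline, the version already used for albumin, with the grade limits printed in the SAP.
- Total protein and IgG: a prespecified worsening margin. Counting any value worse than baseline would flag assay noise in every arm.
- Denominator: all safety-set participants with a baseline and at least one post-baseline value.
- Analytes that the investigator can see: keep the baseline-normal rule.

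The SAP should also say whether the criteria for potentially clinically significant values cover these analytes, and how the Medical Monitor's findings on blinded values enter the adverse event data.

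The cost is SAP wording and one more derivation on data already collected. Somewhat more values will be flagged, including expected IgG falls on active drug, which should be labelled as pharmacodynamic.
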